9.3.4 Removal of Patients from the Study

Patients will be advised that they are free to withdraw from the study at any time for any reason or, if necessary, the Investigator may withdraw a patient from the study to protect the health of that patient. A patient may also be withdrawn for not complying with study procedures. The clinical report will include all reasons for early withdrawals.

All patients who are randomized will be included in the safety analysis comparing the test and placebo products. If a patient terminates from the study early, all efforts will be made to complete the patient's end of study visit procedures. For early termination the Investigator shall fully document the reason for early termination. Reasons for early termination may include the following:

- Patient withdrew consent
- Significant adverse event that led the Investigator or patient to withdraw for safety reasons
- Non-compliance with protocol requirements/protocol deviation (e.g., use of restricted medication, not following dosing procedures, failure to make scheduled study visits in a timely fashion). A patient may also be withdrawn by the Investigator if:
 - A protocol deviation or intercurrent illness occurs during the conduct of the clinical study, which, in the clinical judgment of the Investigator or after discussion with the Sponsor, may invalidate the clinical study

A Randomized, Placebo-Controlled, Double-Blind, Parallel-Group, Multi-Site Phase 2b Clinical Study to Assess the Efficacy, Safety and Tolerability of 8-Week Regimens of Novexatin®, 10% Topical Solution (Taro Pharmaceuticals, USA, Inc.) in Patients with Mild to Moderate Onychomycosis

- It is discovered that the patient was included in the clinical study in contradiction to the inclusion and exclusion criteria
- Pregnancy
- Significant worsening of onychomycosis such that the Investigator and/or patient believes it is in the best interest of the patient to withdraw from the study and be provided alternative treatment
- Adverse event: if a patient reports symptoms, which are considered unacceptable by the patient or the Investigator, he/she will be withdrawn from the clinical study. The appropriate AE form in the Case Report Form (CRF) will be completed.
- Participant enrolls in another clinical trial, or is found to have previously enrolled in this clinical trial

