**Novexatin 10% topical solution**

**Protocol / Study No. NVXT 1404/71442603**

topical solution (Taro Pharmaceuticals USA) for the treatment of mild to moderate distal subungual onychomycosis of the target toenail. Additionally the active formulation in these regimens will be assessed for superiority to a placebo topical solution.

Up to 180 eligible patients with distal subungual onychomycosis who meet all the inclusion criteria and none of the exclusion criteria will be randomized into the study at Visit 2. Patients must be at least 18 years of age, in overall good health. They should have a current diagnosis of distal subungual onychomycosis of mild-moderate severity. Before any study-specific procedures are performed all patients will read and sign the IRB-approved informed consent form.

At least 60 qualified patients in each treatment group will receive randomized and blinded study product. The randomization scheme will be 1:1:1 (Active Treatment A: Active Treatment B: Placebo C). The study products are:

**Test:** Novexatin® 10% Topical Solution (Taro Pharmaceuticals, USA)

**Placebo:** Placebo (Vehicle) Topical Solution (Taro Pharmaceuticals, USA)

Patients will be assigned to one of the three treatment groups:

**Treatment Group A:** Test treatment for Days 1 – 56 and Placebo treatment for Days 281 – 336

**Treatment Group B:** Test treatment for Days 1 – 56 and Days 281 – 336

**Treatment Group C:** Placebo treatment for Days 1 – 56 and Days 281 – 336

Treatment and study durations will be as follows:

**Study Duration:** 365 days (52 weeks)

Patients will undergo evaluation for clinical and mycological cure of onychomycosis at the 7 clinic visits as per study schematic. Randomized patients who withdraw from the study will not be replaced. The study will be conducted according to the following schedule:

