#### **8.3.1 Adverse Events**

All the adverse events (AEs) reported throughout the study will be coded and classified according to the MedDRA (Medical Dictionary for Regulatory Activities) coding dictionary (Version 19.0 or higher). Each adverse event is to be evaluated for date of start and end, seriousness, severity, causal relationship with the study drugs, action taken and outcome.

All AEs will be listed by treatment group and patient.

A summary table of the number and percent of patients with AEs by system organ class, preferred term, and treatment will be presented. Each patient will be counted only once within each preferred term. Other summaries may be added based on the obtained data.

A frequency summary table of the number of AEs by system organ class, preferred term, severity, and treatment will be presented. Severity will be classified as "Mild", "Moderate", or "Severe".

Similarly, a frequency summary table of the number of AEs by system organ class, preferred term, and relationship to a study drug, and treatment will be presented. Relationship to a study drug will be classified as "Not Related" or "Related" where "Related includes "Possible", "Probable", or "Definite".

Should sufficient data exist, adverse event frequencies will be compared between treatments using Fisher's exact test. If the global Fisher's exact test is statistically significant among the three treatment groups at the 5% alpha level (i.e.,  $p < 0.05$ ), then Fisher's exact test using only the Group A and Group B may be performed to identify any potential statistically significant differences that are clinically relevant between the two active treatment groups over the period from Day 1 to Day  $141 \pm 7$  days (i.e., following completion of the first 8 weeks of treatment when both groups have the same test treatment regimen) and over the study duration from Day 1 to Day  $365 \pm 14$  days.

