**8.4 Multiple Comparisons**

No multiple comparison adjustment will be made in this study other than the pre-defined hierarchical testing for the primary and secondary endpoints.

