# P-value will not be presented if the preceding one is  $\geq 0.05$ .

Treatment Group A: Novexatin® 10% Topical Solution for Days 1 – 56 and Placebo (Vehicle) Topical Solution for Days 281 – 336

Treatment Group B: Novexatin® 10% Topical Solution for Days 1 – 56 and Days 281 – 336

Treatment Group C: Placebo (Vehicle) Topical Solution for Days 1 – 56 and Days 281 – 336

Source: Listing L16.2.6.5.1, adeff  
Created on: ddmmmyy hh:mm

Page 1 of N

**T14.3.1.1 Summary of Frequency of All Adverse Events by Body System: Day 1 to Day 141 ± 7  
(Safety Population)**

| Body System                   | MedDRA Term | Treatment Group A
(N = xxx) |                  | Treatment Group B
(N = xxx) |                  | Treatment Group C
(N = xxx) |                  | Fisher's
p-value |
|-------------------------------|-------------|--------------------------------|------------------|--------------------------------|------------------|--------------------------------|------------------|---------------------|
|                               |             | Events                         | Patients
n(%) | Events                         | Patients
n(%) | Events                         | Patients
n(%) |                     |
| Patients with at least one AE | Total       | xx                             | xx (xx.x)        | xx                             | xx (xx.x)        | xx                             | xx (xx.x)        | x.xxxx              |
| Ear and labyrinth disorders   | Ear pain    | xx                             | xx (xx.x)        | xx                             | xx (xx.x)        | xx                             | xx (xx.x)        | x.xxxx              |
|                               | etc.        |                                |                  |                                |                  |                                |                  |                     |

Treatment Group A: Novexatin® 10% Topical Solution for Days 1 – 56 and Placebo (Vehicle) Topical Solution for Days 281 – 336

Treatment Group B: Novexatin® 10% Topical Solution for Days 1 – 56 and Days 281 – 336

Treatment Group C: Placebo (Vehicle) Topical Solution for Days 1 – 56 and Days 281 – 336

Source: Listing L16.2.7.1

Created on: ddmmmyy hh:mm

Page 1 of N

**T14.3.1.2 Summary of Frequency of All Adverse Events by Body System: Day 1 to Day 365 ± 14  
(Safety Population)**

**T14.3.2 Summary of Frequency of All Adverse Events by Relationship  

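### After a significant three-group adverse-event test, the SAP names only an A versus B follow-up; no active-versus-placebo contrast is named, and up to Day 141 A and B are treated alike

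*SAP*

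**What the plan says.** SAP 8.3.1 states: "Should sufficient data exist, adverse event frequencies will be compared between treatments using Fisher's exact test". A follow-up is allowed if the global Fisher's "exact test is statistically significant among the three treatment groups at the 5% alpha level". It is then that a Fisher's "exact test using only the Group A and Group B may be performed", looking for differences between the two active groups. Two windows are given: Day 1 to Day 141 ± 7 and Day 1 to Day 365 ± 14. The SAP describes the first as "following completion of the first 8 weeks of treatment when both groups have the same test treatment regimen".

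The regimens in SAP section 3 confirm this. Group A receives "Test treatment for Days 1 – 56 and Placebo treatment for Days 281 – 336", Group B receives active product in both periods, and Group C receives placebo in both. A and B therefore do not diverge before Day 281.

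No adverse-event test of A versus C, B versus C or (A+B) versus C appears in the SAP text or in the table shells. The shell headed "T14.3.1.1 Summary of Frequency of All Adverse Events by Body System: Day 1 to Day" 141 has one Fisher p-value per row, across all three groups. Protocol 9.3.4 says: "All patients who are randomized will be included in the safety analysis comparing the test and placebo products". On multiplicity, SAP 8.4 says: "No multiple comparison adjustment will be made in this study other than the pre-defined hierarchical testing".

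**The concern.** A significant three-group test says only that the groups are not all alike; a follow-up contrast should show where the difference lies. For Day 1 to 141 the natural question is active versus placebo, with A and B pooled because they have been treated identically. The SAP already uses that contrast for efficacy: comparison 4 of the primary hierarchy in SAP 8.2.1 is (A+B) versus C at Day 141. The safety section, for the same arms and window, splits the identical groups and leaves placebo out.

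If the drug does raise the rate of some event, the planned sequence would typically give a significant global p-value followed by a non-significant A versus B p-value. A reader could take the second as reassurance. Any placebo contrast added later would have been chosen after the data were seen.

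**Working it through.** **Inputs.** 60 patients per group, 1:1:1 (SAP sections 3 and 5). The sample-size section arrives at 60 from 46 / (1 − 0.23) = 59.7. The plan gives no power or expected rate for the adverse-event test, so there is no figure of its own to reproduce, and the rates below are assumptions. All tests are two-sided at p < 0.05.

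**Formulas.** With a, b, c patients with the event in A, B, C, and t = a + b + c:

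- Global test (Fisher-Freeman-Halton): P(a,b,c | t) = C(60,a) · C(60,b) · C(60,c) / C(180,t). The p-value is the sum over all tables with the same t that are no more probable than the observed one.
- Two-group test: P(x,y) = C(n1,x) · C(n2,y) / C(n1+n2, x+y), with n1 = n2 = 60 for pairs, and n1 = 120, n2 = 60 for (A+B) versus C.
- Power: the sum of Bin(a; 60, pA) · Bin(b; 60, pB) · Bin(c; 60, pC) over all 61³ outcomes in which the test is significant. The conditional figures are P(follow-up and global significant) / P(global significant).

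**One concrete outcome.** With 12/60, 12/60 and 2/60: global p = 0.0056, A versus B p = 1.00, (A+B) versus C p = 0.0027, A versus C p = 0.0084.

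**Day 1 to 141 (A and B treated alike).**

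| Assumed rates A/B/C | Global significant | A vs B, given global | (A+B) vs C, given global | (A+B) vs C, unconditional |
|---|---|---|---|---|
| 15/15/5% | 42.3% | 6.0% | 90.5% | 46.2% |
| 20/20/5% | 73.4% | 3.8% | 97.4% | 79.1% |
| 25/25/5% | 91.9% | 3.2% | 99.5% | 95.1% |
| 30/30/10% | 81.9% | 3.8% | 98.8% | 87.8% |

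The detection cost of relying on the global test is the last column minus the second: 3.9, 5.7, 3.2 and 5.9 points. The loss is in attribution far more than in detection.

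**Day 1 to 365 (B has a second active course, A has placebo).**

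| Assumed rates A/B/C | Global significant | A vs B, given global | B vs C, given global | A vs C, given global |
|---|---|---|---|---|
| 15/25/5% | 82% | 25% | 98% | 39% |
| 10/25/5% | 84% | 59% | 97% | 10% |
| 5/20/5% | 75% | 82% | 82% | 1% |

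Here A versus B is informative and worth keeping. In each scenario B versus C is significant at least as often, yet it is not named.

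**Equal rates.** In 4,000 simulated trials with 10% in every group, the global test was significant in 3.7%, so the follow-up would seldom be reached.

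**The case against.** Placebo is part of the planned global test, and the follow-up clause is permissive and forbids no other pair. The protocol's safety analysis section likewise plans testing between treatments without naming pairs, so the SAP does not contradict it. The sentence in Protocol 9.3.4 defines who enters the safety analysis and commits the plan to no particular contrast. A versus B serves a stated aim: the third objective is the safety of the two active regimens. The SAP openly says the regimens coincide in the first window. With three columns of counts beside a significant p-value, the source of a difference will usually be visible. Protocol 7.4 reports few adverse events in earlier studies, at similar rates on active and placebo, so the assumed excess is larger than that history suggests.

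Most of this stands, and it limits the weight of the point. The low A versus B percentages for Day 1 to 141 follow directly from setting A equal to B, but that is what the design does. What does not stand is the idea that permission to add tests is enough: the SAP chose to name one contrast, and for the first window it named one that cannot inform on the drug.

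**Conclusion.** The concern holds, at low severity. SAP 8.3.1 names no active-versus-placebo follow-up, and its one named contrast is uninformative about the drug for Day 1 to 141. Under the assumed rates, when the active groups share an excess over placebo and the global test is significant, A versus B is significant in 3% to 6% of trials and (A+B) versus C in about 91% to 99.5%. These figures rest on 60 evaluable patients per group and on event rates the documents do not supply.

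The consequence is confined to interpretation of exploratory safety results. No decision rule is tied to the follow-up, efficacy testing is untouched, and application site reactions are mostly recorded outside the adverse-event tables (Protocol 9.6.18).

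**What to change.** Replace the follow-up sentence in SAP 8.3.1 with:

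> If the global test is significant (p < 0.05), exploratory, unadjusted Fisher's exact tests will be performed: for Day 1 to Day 141 ± 7, (A+B) vs C; for Day 1 to Day 365 ± 14, A vs C, B vs C and B vs A.

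Add an A+B column and its p-value to shell T14.3.1.1, and the three pairwise p-values to T14.3.1.2. A versus B is dropped only for Day 1 to 141.

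The cost is one SAP paragraph and extra columns in two shells, with no new data. The number of follow-up tests for Day 1 to 141 stays at one. For Day 1 to 365 it rises from one to three, so each term flagged by the global test carries two more unadjusted exploratory p-values. They should be labelled as such.

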**2. OBJECTIVES**

1. Determine the rates of complete therapeutic cure of Novexatin® 10% topical solution (Taro Pharmaceuticals, USA) after daily dosing for one 8-week treatment period (Treatment Group A) and two 8-week treatment periods separated by a 32-week rest period (Treatment Group B), and Placebo (vehicle) topical solution (Taro Pharmaceuticals, USA) after two 8-week treatment periods separated by a 32-week rest period (Treatment Group C), at three test-of-cure visits (Day 141, Day 281 and Day 365) in patients with mild to moderate distal subungual onychomycosis of the target toenail.
2. Compare rates of complete therapeutic cure between Treatment Groups according to a hierarchical evaluation scheme detailed in the statistical sections.
3. Evaluate safety and tolerability of the two regimens of Novexatin® 10% topical solution (Treatment Groups A and B) in patients with mild to moderate distal subungual onychomycosis of the target toenail.

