**Novexatin 10% topical solution**

**Protocol / Study No. NVXT 1404/71442603**

49%. The rate of therapeutic cure for placebo is expected to be approximately 21%. Approximately 46 patients in each treatment group in the ITT population will provide over 80% power to show a difference at  $p < 0.05$  (two-sided Z test and a pooled response rate for the standard error of the difference in proportions) between each of the active treatment groups and the placebo group. To allow for a 23% drop-out rate, a total of 180 patients will be enrolled in the study, with up to 60 patients in each of the treatment groups.

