**Safety Population**

All patients who were randomized and received study product will be included in the Safety population.

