**8. STATISTICAL ANALYSIS METHODS**

If not otherwise specified, statistical significance is defined as  $p < 0.05$  and is two-tailed. Data will be summarized with respect to demographic and baseline characteristics and safety variables.

For categorical variables, the number and percent of each category within a parameter will be calculated for non-missing data. For continuous variables, statistics will include n, mean, standard deviation, median, minimum and maximum values.

All statistical analyses will be conducted using SAS®, Version 9.4 or higher. Datasets will be prepared using headings from Clinical Data Interchange Consortium (CDISC) Study Data Tabulation Model (SDTM) implementation for human clinical trials and ADaM (Analysis Dataset Model).

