### **8.3 Safety Analysis**

All study patients who are randomized to the active treatment period of the study, and received study product will be included in the comparative safety analysis. The safety profile of each treatment group will be evaluated by comparing adverse events, application site reactions, vital signs and changes in clinical laboratory results obtained throughout the study. Data will also be collected during the study to compare the results of the KOH stains to the mycological culture results observed during the study.

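### The adverse-event comparison of the two regimens has no risk difference, no confidence interval and no second-course window, and its only A versus B test is optional and gated

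*SAP*

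**What the plan says.** The third objective in SAP section 2 is to "Evaluate safety and tolerability of the two regimens of Novexatin", that is, one 8-week course (Group A) and two (Group B). SAP 8.3 adds: "The safety profile of each treatment group will be evaluated by comparing adverse events".

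SAP 8.3.1 sets out the adverse-event (AE) inference, to be done if the data suffice:

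- Gate: "If the global Fisher's exact test is statistically significant among the three treatment groups at the 5% alpha level".
- Second step: "then Fisher's exact test using only the Group A and Group B may be performed", over Day 1 to Day 141 and over Day 1 to Day 365.
- Purpose: "to identify any potential statistically significant differences that are clinically relevant between the two active treatment groups".

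Shell T14.3.1.1 (Day 1 to 141) has events and patients n (%) per group and one Fisher p-value column. T14.3.1.2 (Day 1 to 365) is given by title only, directly after that shell. Neither has a difference or an interval. The efficacy shells (Table V and those like it) do have a difference column.

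The Safety Analysis section of the protocol plans a Fisher or similar test with no gate. SAP 8.7, which lists changes from the protocol's analysis, does not mention that one was added.

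**The concern.** Groups A and B receive the same product until the second course, so B against A is the direct randomised evidence on whether that course adds harm. Three features weaken the planned comparison.

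1. **No estimate.** The formal output is a p-value. Nothing shows how large an excess the data still allow.
2. **The windows miss the question.** Up to Day 141 the regimens are identical, so that window cannot inform on the second course. Day 1 to 365 mixes second-course events with about 280 days before it begins. No AE table starts at the second course.
3. **The pairwise test may never be run.** It depends on a three-group test and is then optional.

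At stake is how Objective 3 is answered, in a trial whose results feed the planning of Phase 3.

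**Working it through.** **Inputs from the documents**

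- Group size: "with up to 60 patients in each of the treatment groups" (SAP section 5), 1:1:1 allocation.
- Safety population: "All patients who were randomized and received study product will be included in the Safety" population (SAP section 7), so 60 per group is the right order.
- Significance: p < 0.05, "and is two-tailed" (SAP section 8).
- AE rates: none given. The protocol's summary of clinical studies reports only a low incidence. All AE rates below are assumptions.

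**The plan's own figure (efficacy)**

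Rates 49% and 21%, 46 per group, pooled rate 0.35.

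- Null SE = √(2 × 0.35 × 0.65 / 46) = 0.0995.
- Alternative SE = √((0.49 × 0.51 + 0.21 × 0.79) / 46) = 0.0951.
- Power = Φ((0.28 − 1.96 × 0.0995) / 0.0951) = Φ(0.89) = 81.5%, which agrees with over 80%.
- Drop-out: 46 / (1 − 0.23) = 59.7, so 60.

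The size was set for a 28-point efficacy difference. No AE power is claimed.

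**Illustration for AEs**

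Method: enumerate all outcomes of three independent binomials with n = 60. Count those with three-group Fisher (Freeman-Halton) p < 0.05, those with A versus B Fisher p < 0.05, and those with both. Assume 5% in A and C and 15% in B over the whole study.

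| Criterion | Probability |
|---|---|
| Three-group test significant | 44.6% |
| Both tests significant | 31.1% (miss 68.9%) |
| A versus B alone, no gate | 32.6% (miss 67.4%) |

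The gate costs 68.9 − 67.4 = 1.5 points. The rest is sample size: 80% power for 5% against 15% needs about 141 per group (160 with continuity correction).

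**Dependence on the assumed base rate**

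Gated miss rate for a tripled whole-study rate, with C equal to A:

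| A to B | Miss |
|---|---|
| 1% to 3% | 99.5% |
| 2% to 6% | 94.5% |
| 3% to 9% | 86.4% |
| 5% to 15% | 68.9% |
| 10% to 30% | 28.8% |
| 15% to 45% | 6.6% |
| 20% to 60% | 0.6% |

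**Excess confined to the second course**

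Assume 5% per course, independent courses, and a tripled rate in B's second course only.

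- A and C: 1 − 0.95² = 9.75%.
- B: 1 − 0.95 × 0.85 = 19.25%.

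On the planned Day 1 to 365 comparison both tests are significant 19.9% of the time, a miss of 80.1%.

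**What an interval would show**

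Suppose 9/60 in B and 3/60 in each of A and C.

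- Three-group p = 0.104, so the A versus B test is not run; it would give p = 0.125.
- Wilson limits: 8.1% to 26.1% for 9/60, and 1.7% to 13.7% for 3/60.
- Newcombe lower = 10.0 − √((15.0 − 8.1)² + (13.7 − 5.0)²) = −1.1 points.
- Newcombe upper = 10.0 + √((26.1 − 15.0)² + (5.0 − 1.7)²) = +21.6 points.

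The planned table would show 15% against 5% and p = 0.10. The interval adds that an excess of 20 points is still compatible with the data. With 3/60 in both groups it would run from −9.3 to +9.3.

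**The case against.** Only the pairwise p-value is gated. Patients n (%) by group, events by severity and relationship, and serious events are tabulated regardless. Anyone can compute an interval from the counts, and the AE listing carries start dates. Local reactions matter most for a topical product, and by default they are not recorded as AEs. They are graded at each visit and tabulated by group in T14.3.9. That table includes Visit 6, at the end of the second course, and Visit 7, four weeks later. Low AE power is ordinary in a phase 2b trial sized for efficacy, and an interval adds none. The sentence on the A versus B test also asks for clinical relevance, not significance alone.

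All of this stands. It rules out two stronger readings that a reader might infer:

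- **That the plan will report a non-significant result as no difference.** Neither document says so, and Objective 3 is to evaluate safety, not to show that the regimens are equally safe.
- **That the gate is why a real excess would be missed.** It accounts for about 1.5 points of the 68.9% in the illustration.

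The objection does not remove the gap in the planned output. An interval that a reader could work out is not one that the report commits to. T14.3.9 does not cover events recorded as AEs, and no AE summary isolates the second course.

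**Conclusion.** The point holds as a gap in estimation and in the time window. The A versus B AE test is optional and conditional, no risk difference or interval is planned, and no AE window starts at the second course. The formal comparison therefore says little about added harm from that course, while the descriptive tables remain available.

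The figure of about 31% for both tests rests on 60 per group and on assumed whole-study rates of 5%, 15% and 5% in A, B and C. It should be cited only with those assumptions. A reader might take the corresponding 69% miss as the general figure for a tripled rate, or for a tripling in the second course alone. Neither is supported. The first runs from over 99% to under 1% for base rates of 1% to 20%. The second is about 80% under the per-course assumption above. The change is worth making because it serves a stated objective at almost no cost.

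**What to change.** In SAP 8.3.1 and T14.3.1.2:

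1. Report the B minus A risk difference with a 95% confidence interval (for example Newcombe), whatever the Fisher p-value. Do this for patients with at least one AE and for each preferred term above a frequency fixed in advance.
2. Give it for Day 1 to 365, and for AEs with onset from the start of the second course (about Day 281) to Day 365. The AE listing already holds onset dates, and the compliance listing (L16.2.5) holds the first dose date of Period 2. State the denominator for this window, for example patients who started the second course.
3. Label the intervals descriptive and unadjusted, and keep the Fisher p-values as descriptive flags.
4. State that p >= 0.05 is not evidence of equal safety.

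Cost: SAP wording, a few columns and one more AE window, with no new data or patients. The downside is that a few more chance differences will be displayed. The intervals show the uncertainty but do not add power.
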